9.3 CLINICAL LABORATORY EVALUATIONS

Clinical laboratory tests (hematology, serum chemistry, fecal chemistry, and LIGHT [serum and tissue]) will be summarized from baseline through Visit 10/ET by visit. For each individual lab test value, the observed value and change from baseline will be summarized by disease and cohort.

All results, along with urinalysis and other laboratory tests, will be listed.

Other laboratory tests include cytokines (e.g. IL-1 beta, IL-6, IL-8, and TNF-alpha, and other exploratory cytokines), flow cytometry analysis of peripheral blood leukocytes, and RNA sequencing.

9.4 VITAL SIGNS

Vital signs results including systolic and diastolic blood pressure (mmHg), pulse rate (beats/min), respiratory rate (breaths/min), and body temperature (C) will be listed for individual subjects. These will be collected at Visits 1 (Screening), 2 (Day 0), 4 (Day 14), 6 (Day 28), 8 (Day 42), 10/ET (Day 56).

Summary statistics, including change from baseline, will be determined for each measure, and will be summarized by disease, cohort and by visit and time point (pre-/post-dose).

9.5 PHYSICAL EXAMINATION

A complete physical examination including all major body systems will be performed at Visits 1 (Screening), 2 (Day 0), 6 (Day 28), and 10/ET (Day 56). In addition, a brief physical exam will be performed at Visits 4 (Day 14) and 8 (Day 42).

Physical examination results will be listed for individual subjects.

9.6 ECG EXAMINATION

ECG examination will be assessed at Visits 1 (Screening), 6 (Day 28), and 10/ET (Day 56).

Observed values and changes from baseline for ECG parameters, including abnormal results and significance, will be displayed by disease, cohort, and time point. All ECG data will be listed, including shifts from normal at baseline to abnormal post-baseline.

9.7 PREGNANCY TEST

Pregnancy tests (for female subjects of childbearing potential) will be performed at Visits 1 (Screening), 2 (Day 0), 6 (Day 28), and 10/ET (Day 56).

Urine test results will be presented on the urinalysis listing while serum test results will be presented on the serum chemistry listing. Each test result will be defined to be "negative" or "positive".

10. PK ANALYSIS

PK concentration data will be presented in a by-subject listing and summarized by disease, cohort and visit using continuous summaries for the PK analysis set. Continuous summaries will include arithmetic as well as geometric statistics: n, mean, standard deviation, coefficient of variation, median, minimum, maximum, geometric mean, geometric standard deviation, and geometric coefficient of variation.

Plasma concentrations that are reported as lower limit of quantification (LLOQ) will be set to 0 (zero) for reporting and summary statistics, except for geometric mean and error, for which only nonzero data is included.

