12.1.5.6. Visit 10 (Day 56 [\pm 3 days])

Subjects will return to the clinic on Day 56 (\pm 3 days), at which time the following procedures will be performed:

1. Perform a complete physical examination, including measurement of weight
2. Collect vital signs, including systolic and diastolic blood pressures, pulse, respiration rate and temperature
3. Perform 12-lead ECG
4. Collect blood sample for clinical laboratory tests
5. Collect blood samples for plasma MDGN-002 concentration, PK and ADA analysis
6. Collect blood sample for exploratory analyses as defined in [Table 1](#)
7. Collect stool for fecal calprotectin analysis
8. Collect urine sample for urinalysis
9. Collect urine sample for urine β -hCG test (for females of childbearing potential only)
10. Administer the CDAI (CD only)
11. Review diary completion
12. Administer IBD-Q questionnaire
13. Conduct the endoscopy and biopsy
14. Calculate the Modified Mayo Score (excluding the PGA component) using the endoscopy score from the central reader and the diary data on stool frequency and rectal bleeding (UC only)
15. Assess and record any AEs and concomitant medications
16. Assess subject response and available results against individual stopping rules criteria defined in [Section 8.5.1](#).

In addition, ongoing AEs from the previous visit will be assessed and any change in their status will be recorded.

NOTE: Stool samples may be obtained at any time during the visit.

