12.1.6. Early Termination

If a subject is withdrawn from the study for any reason, every effort must be made to conduct all Day 56 (Visit 10) procedures and assessments (see [Section 12.1.5.6](#)).

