12.1.7. Safety Follow-Up

12.1.7.1. Visit 11 (Day 84 [± 3 days])

Subjects will return to clinic 28 days (± 3 days) after Visit 10 or the early termination visit for a safety follow-up visit, as appropriate. Subject will have blood collected for plasma MDGN-002 concentration, PK and ADA analyses. Any concomitant medications and newly occurring AEs since the last visit will be recorded. In addition, ongoing AEs from the previous visit will be assessed and any change in their status will be recorded.

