12.3.2.1. Blood Sample Collection and Analysis

Blood samples will be collected within 60 minutes prior to the administration of MDGN-002 on Days 0, 14, 28 and 42 (Visits 2, 4, 6, and 8 respectively) and at any time on Days 7, 21, 35, 49, 56, and 84 (Visits 3, 5, 7, 9, 10, and 11) and processed to plasma (see laboratory manual). Time of PK samples will be recorded in the electronic CRF. A total of 1.0mL plasma (0.5 mL per PK and ADA sample) will be collected from each subject to measure plasma concentrations of

MDGN-002 or ADA samples. Pharmacokinetic and ADA samples will be processed according to the methods and directions set forward in the Laboratory Manual(s) and guidance(s).

Pharmacokinetic and ADA plasma sample analysis will be performed by laboratory defined in the Laboratory Manual(s) and guidance(s), according to their SOPs using a validated enzyme-linked immunosorbent assay (ELISA). Assay and analysis details will be described in the method validation and bioanalytical information.

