2. STUDY DESIGN AND PROCEDURES

This is a Phase 1b, open-label, dose-escalation, signal-finding, multi-center study to evaluate the safety, tolerability, pharmacokinetics, and short-term efficacy of MDGN-002 in adults with moderate to severe, active CD or UC who have previously failed anti-TNFα treatment. The study is a pilot study using a dose-escalation design to characterize the safety and tolerability of 2 different doses of MDGN-002 (1.0 mg/kg and 3.0 mg/kg) in the CD population, and 3.0 mg/kg in the UC population. All subjects will receive a total of 4 doses of MDGN-002 by SQ injection at 14-day intervals. The study will consist of a screening period, an open-label treatment period and a safety follow-up visit.

In this document, MDGN-002 will be referred to as "study drug" regardless of dosage, and "cohort" will refer to 1.0 mg/kg (Cohort 1) or 3.0 mg/kg (Cohort 2) as described above.

The following study visits will be performed:

- Visit 1 (Screening). This period may be up to 14 weeks, inclusive of a washout period for subjects who have received a biologic treatment within 12 weeks of Visit 1. The amount of time required is determined based on the subject's last dose of the medication and may be up to 12 weeks.
- Visit 2 (Pre-/Post-Dose Day 0);
- Visit 3 (Day 7);
- Visit 4 (Pre-/Post-Dose Day 14);
- Visit 5 (Day 21);
- Visit 6 (Pre-/Post-Dose Day 28);
- Visit 7 (Day 35);
- Visit 8 (Pre-/Post-Dose Day 42);
- Visit 9 (Day 49);
- Visit 10 (Day 56/Early Termination (ET));
- Visit 11 (Day 84 or 28 days after ET).

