6.1.3 Pharmacokinetic Analysis Set

The Pharmacokinetic (PK) Analysis Set will include all subjects who receive at least one dose of study drug and for whom plasma concentration data are available, minimally at baseline and one post-baseline visit.

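### SAP 10 summarises concentrations by visit, so any early-termination samples would be averaged with four-dose Day 56 and Day 84 levels

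*SAP*

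**What the plan says.** SAP Section 10 and Table 14.1.6 report concentrations "summarized by disease, cohort and visit using continuous summaries for the PK analysis set". The visits are defined in SAP Section 2, where one label is "Visit 10 (Day 56/Early Termination (ET" and the next is "Visit 11 (Day 84 or 28 days after ET".

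The protocol draws PK blood at both. At early termination, "every effort must be made to conduct all Day 56 (Visit 10) procedures and assessments" (Protocol 12.1.6), and the Visit 10 list includes "Collect blood samples for plasma MDGN-002 concentration, PK and ADA analysis" (Protocol 12.1.5.6). Another PK sample is taken 28 days "after Visit 10 or the early termination visit for a safety follow-up visit" (Protocol 12.1.7.1).

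The PK analysis set takes in "all subjects who receive at least one dose of study drug and for whom plasma concentration data are available", with the further condition of a baseline and at least one post-baseline concentration (SAP 6.1.3). An early terminator who meets that condition stays in. The protocol's PK population (Section 13.1.1) refers to the assigned dose but does not say all four doses.

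SAP 5.8 works with nominal visits and exempts only diary data. Its wording covers safety and efficacy summaries and does not mention PK. Neither document gives ET samples their own row, reassigns them by time since dose, or limits the Day 56 and Day 84 rows to subjects with four doses.

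**The concern.** For an efficacy score, a pooled Day 56/ET row can be defended as a last observation on treatment. A concentration is different: it depends directly on how many doses were given and how long ago. SAP 5.3 puts the half-life at 18 to 27 days against a 14-day dosing interval, so the drug accumulates over the four doses. A sample taken after one or two doses does not measure what a Day 56 sample measures.

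Estimating plasma concentrations is a secondary objective. The Day 56 row shows the level one dosing interval after the fourth dose. Day 84 is the only scheduled sample taken more than one interval after the final dose. With four Crohn's subjects per dose level, one non-comparable value can move the mean and produce spread that looks like between-subject variability.

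**Working it through.** The plan gives no PK figure to reproduce, and the sample size rests on feasibility. What follows is an illustration.

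**Inputs from the documents**
- Half-life h = 18.0 to 27.0 days (SAP 5.3)
- Doses on Days 0, 14, 28 and 42 (Protocol 10.1)
- 4 Crohn's subjects per dose cohort and 6 UC subjects at 3 mg/kg (Protocol 8.7)
- Subjects who withdraw before the third dose may be replaced (Protocol 8.7 and 9.6)

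**Assumptions not in the documents**
- One compartment, linear kinetics, absorption complete by sampling
- No between-subject variation
- ET 14 days after the last dose (varied below), one early terminator per group

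**Step 1: decay over one interval.** r = 2^(−14/h), which is 0.583 at 18 days and 0.698 at 27 days.

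**Step 2: four-dose level at Day 56**, relative to one dose after 14 days. 1 + r + r² + r³ = 2.12 at 18 days and 2.53 at 27 days.

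**Step 3: ET level after m doses as a fraction of the four-dose level.** For ET g days after the last dose, the fraction is 2^(−(g−14)/h) × (1 + … + r^(m−1)) / (1 + r + r² + r³).

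| Doses received | ET at 14 days, h = 18 | ET at 14 days, h = 27 | ET at 7 to 28 days, both h |
|---|---|---|---|
| 1 | 0.471 | 0.396 | 0.28–0.62 |
| 2 | 0.746 | 0.672 | 0.44–0.98 |
| 3 | 0.906 | 0.865 | 0.53–1.19 |

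The fractions are the same for Visit 11 when it falls 28 days after Visit 10 or ET, because numerator and denominator both decay by 2^(−28/h).

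**Step 4: effect on the row.** With n−1 subjects at 1 and one at fraction f, the mean is 1 − (1−f)/n, the SD is (1−f)/√n, and the CV is SD/mean. For a one-dose terminator with ET at 14 days:

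| Row | Fall in mean | CV |
|---|---|---|
| Crohn's, not replaced, n = 4 | 0.529/4 = 13% to 0.604/4 = 15% | 30–36% |
| Crohn's, replaced, n = 5 | 0.529/5 = 11% to 0.604/5 = 12% | 26–31% |

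In the UC cohort without replacement (n = 6) the mean falls by 9–10%. The geometric mean, which SAP 10 also reports, falls by 17–21% at n = 4. For a two-dose terminator the Crohn's mean falls by 6–8% at n = 4, and by 0.254/5 = 5% to 0.328/5 = 7% at n = 5.

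**Step 5: effect on the dose contrast.** Suppose exposure were exactly dose-proportional, with one unreplaced one-dose terminator. The threefold ratio of 3 to 1 mg/kg would read 3 × 0.849 = 2.55 to 3 × 0.868 = 2.60 if the terminator is in the 3 mg/kg Crohn's cohort. It would read 3/0.868 = 3.46 to 3/0.849 = 3.53 if in the 1 mg/kg cohort.

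**The case against.** The strongest reply is that the problem is conditional, partly inferred, and visible to a careful reader.

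- **Conditional.** A reader might infer from the replacement rule that early-termination records are expected. The documents do not say so: they provide for withdrawal as a contingency, and ET sampling is a best-effort procedure. This stands. It does not remove the need for a rule, since one chosen after seeing the concentrations would be post hoc.
- **Size.** A reader might take 13–15% as the size of the effect. That needs a one-dose terminator who is not replaced and is sampled 14 days after dosing. A two-dose subject sampled at 7 days is at 0.81–0.98 of the four-dose level, and a three-dose subject at 7 days is slightly above it (1.04–1.19). This stands.
- **Placement.** SAP 5.8 does not name PK. Placement in the Day 56 and Day 84 rows rests on the visit labels in SAP 2 and the by-visit rule in SAP 10. SAP 1 allows for a separate PK document as needed. These points are fair, but no other placement is given, and Table 14.1.6 is already committed.
- **Harm.** A reader might infer that the dose comparison is lost. The documents do not support that. No test is planned, the two doses would remain clearly apart (Step 5), and the rows for Visits 3 to 9 receive no ET or post-ET samples. The planned median would be unchanged in the Step 4 example, and the by-subject listings would show any affected value. All this limits the harm but leaves the means and CVs in the two rows uncorrected.

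**Conclusion.** The concern holds in conditional form. As written, the SAP pools samples that differ in doses received or time since dose in the Visit 10 and Visit 11 rows whenever a subject terminates early and gives those samples. With no early terminators the effect is zero.

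If one Crohn's subject stops after a single dose and is sampled 14 days later, the cohort's Day 56 mean falls by 13–15% without replacement or 11–12% with it, with a CV of 30–36% or 26–31% from that subject alone. Later termination usually matters less, though the time of sampling can change both size and direction. The half-life comes from SAP 5.3. The kinetic model, the absence of between-subject variation and the ET timing are assumptions.

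It would go too far to say that the PK set takes anyone with one dose, because a baseline and a post-baseline concentration are also required. Nor are data lost: the defect is in the summary table, and the listings keep every value.

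**What to change.** In SAP 10 and Table 14.1.6:

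1. Include a sample in the Day 56 or Day 84 row only if the subject received all four doses and the sample falls within ±3 days of the scheduled time since the fourth dose: 56 − 42 = 14 days, or 84 − 42 = 42 days.
2. Place any other ET or post-ET sample in the scheduled row that matches both doses received and time since last dose within ±3 days, but only if that subject has no scheduled sample in that row. Otherwise list it only. For example, an ET sample 14 days after the first dose fits the pre-dose Visit 4 row if that row is empty for the subject.
3. Add doses received and days since last dose to Listing 16.2.5.2.

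No new data are needed. The SAP already derives the number of doses (Section 7) and treatment completion as four doses (Section 6.2), and "Time of PK samples will be recorded in the electronic CRF" (Protocol 12.3.2.1).

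The main cost is a smaller n in the two rows if anyone terminates early. Rule 1 can also drop a completer. With each visit allowed ±3 days around Day 0 timing, the gap from the fourth dose to Visit 10 can run from 53 − 45 = 8 to 59 − 39 = 20 days. The sponsor should accept that loss or confine the window test to ET and post-ET samples, and decide before database lock.

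Two points remain. A missed dose in a continuing subject would still mix dose counts in the intervening rows. Protocol 8.1, 8.2.3 and 12.2 also describe follow-up as about 28 days after the final dose; this must be reconciled with Day 84 before the 42-day window is programmed.

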11. ADA ANALYSIS

Anti-drug Antibodies (ADA) data will be collected at Visits 2 (Day 0), 4 (Day 14), 6 (Day 28), 10 (Day 56/ET), and 11 (Day 84 or 28 days after ET). Screening result, confirmation result, and titration result using the safety analysis set will be presented in a by-subject listing.

12. INTERIM ANALYSIS

No interim analyses will be performed.

13. DATA MONITORING COMMITTEE

An external, independent Data Monitoring Committee (DMC) comprising physicians, scientists and a biostatistician will review the study data at separate meetings after enrollment in the first and second cohorts, respectively.

The DMC's role is to protect the interests of the subjects in the study and those still to be entered in the study by reviewing information such as safety, tolerability, pharmacokinetic and efficacy data.

Additional details will be outlined in the DMC charter.

14. CHANGES TO THE ANALYSES PLANNED IN THE PROTOCOL

Not applicable.

15. TABLE OF CONTENTS FOR APPENDICES

15.1 TABLES

Table Number	Analysis Set	Title	
14.1.1	All Subjects	Patient Disposition	
14.1.2	Safety	Important Protocol Deviations	
14.1.3	Safety	Demographics and Baseline Characteristics	
14.1.4	Safety	Prior Medications by ATC Class and Preferred Term	
14.1.5	Safety	Concomitant Medications by ATC Class and Preferred Term	
14.1.6	PK	Pharmacokinetic Concentration	
14.2.1	FAS	Simple Endoscopy Score for Crohn's Disease (SES-CD)	
14.2.2	FAS	Modified Mayo Score for Ulcerative Colitis	
14.2.3	FAS	Ulcerative Colitis Subject Diary	
14.2.4	FAS	Crohn's Disease Activity Index (CDAI) Item and Total Scores	
14.2.5	FAS	Crohn's Disease Subject Diary	
14.2.6	FAS	Inflammatory Bowel Disease Questionnaire (IBD-Q)	
14.3.1	Safety	Study Drug Exposure	
14.3.2.1	Safety	Overall Summary of Treatment Emergent Adverse Events	
14.3.2.2	Safety	Treatment Emergent Adverse Events by System Organ Class and Preferred Term	
14.3.2.3	Safety	Study Drug Related Treatment Emergent Adverse Events by System Organ Class and Preferred Term	
14.3.2.4	Safety	Treatment Emergent Adverse Events by Preferred Term	
14.3.2.5	Safety	Treatment Emergent Adverse Events by System Organ Class, Preferred Term, and Severity	
14.3.3.1	Safety	Hematology Parameters	
14.3.3.2	Safety	Chemistry Parameters	
14.3.3.3	Safety	Fecal Chemistry Parameters	
14.3.4.1	Safety	Soluble LIGHT Levels	
14.3.4.2	Safety	Tissue LIGHT Levels	
14.3.5	Safety	Vital Signs	
14.3.6	Safety	Electrocardiogram (ECG)	

15.2 LISTINGS

Listing Number	Analysis	Title
	Set	

16.2.1.1	All Subjects	Subject Disposition
16221		Subjects Not Meeting Inclusion / Meeting
16.2.2.1	All Subjects	Exclusion Criteria
16.2.2.2	All Subjects	Protocol Deviations
16.2.3	All Subjects	Study Populations
16.2.4.1	Safety	Demographics and Baseline Characteristics
16.2.4.2.1	Safety	Medical History
16.2.4.2.2	Safety	Crohn's Disease History
16.2.4.2.3	Safety	Ulcerative Colitis History
16.2.4.3	Safety	Prior and Concomitant Medications
16.2.5.1	Safety	Drug Administration and Accountability
16.2.5.2	PK	Pharmacokinetic Sample Collection and Concentration
16.2.5.3	Safety	Anti-drug Antibodies (ADA)
16.2.6.1.1	FAS	Quantitative Endoscopy (SES-CD) and Biopsy – Part 1
16.2.6.1.2	FAS	Quantitative Endoscopy (SES-CD) and Biopsy – Part 2
16.2.6.2.1	FAS	Modified Mayo Score for Ulcerative Colitis
16.2.6.2.2	FAS	Ulcerative Colitis Subject Diary
16.2.6.3.1	FAS	Crohn's Disease Activity Index (CDAI) Scores
16.2.6.3.2	FAS	Crohn's Disease Subject Diary
16.2.6.3.3	FAS	Crohn's Disease Activity Index (CDAI) Non- Diary Item Data and Related Questions
16.2.6.4	FAS	Inflammatory Bowel Disease Questionnaire (IBD-Q)
16.2.7.1	Safety	Adverse Events
16.2.7.2	Safety	Serious Adverse Events
16.2.7.3	Safety	Adverse Events Leading to Discontinuation
16.2.8.1	Safety	Hematology Laboratory Results
16.2.8.2	Safety	Serum Chemistry Laboratory Results
16.2.8.3	Safety	Fecal Chemistry Laboratory Results
16.2.8.4	Safety	Urinalysis Laboratory Results
16.2.8.5	Safety	LIGHT and Confirmatory Disease Biopsy Results
16.2.8.6	Safety	Other Laboratory Results
16.2.9.1	Safety	Vital Sign Measurements
16.2.9.2	Safety	Physical Examination
16.2.9.3	Safety	12-Lead Electrocardiogram (ECG)

